#### 7.2.1.2.3 *Procedures for Reporting Pregnancies*

Any pregnancy occurring during the clinical study, where the fetus could have been exposed to study product, must be monitored until its outcome in order to ensure the complete collection of safety data.

Subjects who have a positive pregnancy test during the screening period are considered screen failures and are recorded as such in the eCRF, and no pregnancy form is to be completed.

If a subject becomes pregnant after receiving study medication, the Investigator is to do the following:

1. The subject does not need to be withdrawn from the clinical study, i.e., she may continue to attend the planned study visits, but no invasive procedure should be conducted (e.g., no sample should be taken for lab testing).
2. Complete the Pregnancy Report Part A as fully as possible. Send the form within 24 hours of receipt of the information to the Safety e-mail (listed in Section 7.2.1.2.2).
3. Monitor and record the progress of the pregnancy until its outcome. If necessary and approved by the subject or their legal healthcare representative, contact the subject's regular physician (general practitioner or gynecologist) or hospital staff to obtain further details and ask for regular follow-up information.
4. At the outcome of the pregnancy, complete the Pregnancy Report Part B. For all additional evaluations, send the follow-up information to the Safety e-mail within 24 hours of receipt of the information. If the subject can no longer be reached (lost to follow-up), documentation of

	Title 05PF2005 Clinical Study Protocol - STAR	Doc id MA-48441
--	--	----------------------------------

the non-response/attempted contact consisting of, e.g. calling three times at different hours and leaving messages, is required.

5. If the pregnancy leads to an abortion (elective abortion, spontaneous abortion or therapeutic abortion), *in utero* death or congenital anomaly, follow the procedure for declaration of an SAE (see Section 7.2.1.2.2).

### 7.3 Other Assessments

#### 7.3.1 Photography

Standardized digital photographs will be taken of the subject's glabellar region and the full face at Visit 2 (baseline, prior to treatment), Visit 3, 4 and 6.

Each Investigator (or designee) will take photographs using the site's camera equipment, conditions, and settings. Detailed instructions for photography will be provided in a separate photography manual.

#### 7.3.2 Pregnancy Test

For females of childbearing potential, a urine pregnancy test will be performed prior to treatment at screening and baseline (prior to treatment). A negative pregnancy test is required for study inclusion. The result will be documented. Pregnancies during the study should be reported as described in Section 7.2.1.2.3.

### 7.4 Appropriateness of Measurements

The type of efficacy and safety measurements chosen for this study have been used in previous clinical studies and are considered to be adequate measurements that are widely recognized as reliable, accurate, and relevant for the target indication and study objective.

## 8. CLINICAL STUDY VISITS DESCRIPTIONS AND PROCEDURES

### 8.1 Description of Clinical Study Visits

For an overview of the schedule of assessments for each study visit, please refer to [Table 2](#).

A written, signed ICF must be obtained prior to performing any clinical study-related evaluations and/or procedures. The subject must be provided with a fully completed, dated and signed copy of the ICF.

 EST. 1981	Title 05PF2005 Clinical Study Protocol - STAR	Doc id MA-48441
---	--	----------------------------------

### 8.1.1 Screening, Visit 1 (Day -21 to Day 0)

The screening and baseline visits may be performed on the same day; however, a maximum of 21 days is allowed between the screening and baseline visits.

At the screening visit, the Investigator or designee will:

1. Review and explain the nature of the study to the subject, particularly the prohibited activities and constraints (e.g., restrictions for other aesthetic treatments and the use of topical and systemic medications, see Section 5.4.5).
2. Obtain the signed and dated ICF, and provide the subject with a fully completed, dated and signed copy of the ICF.
3. Collect information regarding demographics (i.e., date of birth, gender, race, ethnicity, height, and weight), relevant medical history and concurrent diseases, previous facial treatments/procedures (including toxin naïve/non-toxin naïve), previous medications and procedures, and concomitant medications and procedures (see Table 2).
4. If the subject is a female of childbearing potential, collect urine for pregnancy test and document the test result (see Section 7.3.2). A negative result is required for study inclusion.
5. Investigator assigns a screening number to all subjects, reviews the inclusion/exclusion criteria (Sections 5.2.1 and 5.2.2), and confirms whether or not the subject meets study eligibility requirements.
  - If yes, schedule the baseline visit.
  - If no, document the subject as a screen failure.

### 8.1.2 Baseline/Treatment, Visit 2 (Day 0)

If the screening and baseline visits are performed on the same day, the study assessments that are common to both study visits will only be performed once (i.e., AE, concomitant therapies/procedures, UPT, inclusion/exclusion review). A maximum of 21 days is allowed between the screening and baseline visits.

At the baseline visit, the Investigator or designee (*Note: the treating investigator must perform both the reconstitution/preparation and the treatment*) will:

1. Ask the subject about any changes in his/her concomitant therapies/procedures (added, removed or changed) since the previous visit. Record changes in concomitant therapies/procedures as appropriate (Section 5.4).
2. If the subject is a female of childbearing potential, collect urine for pregnancy test and document the test result (see Section 7.3.2). A negative result is required for study inclusion.
3. Investigator reviews the inclusion/exclusion criteria (Section 5.2.1 and 5.2.2), and confirm whether or not the subject meets study eligibility requirements.
  - If yes, enroll/randomize the subject in the clinical study. Proceed to the next steps.

GALDERMA EST. 1981	Title 05PF2005 Clinical Study Protocol - STAR	Doc id MA-48441
-----------------------	---	---------------------------

Effective date: 2021-12-01 17:39

Effective

Version: 5.0

- If no, document the subject as a screen failure.

4. For subjects who meet all eligibility requirements, the Investigator will receive notification of the subject's randomization assignment.
5. Take subject photographs (see Section 7.3.1) for future GAIS assessments according to separate photography manual. If the subject is wearing make-up, instruct the subject to remove it prior to taking the photographs.
6. Make sure to equilibrate Alluzience, or the saline used for reconstitution of powder BoNT-A, for 30 min to room temperature before injection.
7. Ask the subject to complete the Subject Satisfaction Questionnaire (Appendix 6). **Note:** must be performed before treatment.
8. The Investigator should prepare Study Product according to the assigned treatment in the same room and in front of the subject (Section 6.1.7).
9. Prior to injection, clean the subject's treatment area with a suitable antiseptic solution.
10. The Investigator will administer treatment. See Section 6.1.7.1 for injection technique and treatment procedure requirements.
11. Ask the subject about any Aes experienced, in connection to, and after the treatment. Record Aes, as appropriate, on the corresponding eCRF form(s).
12. Record post-treatment concomitant therapies/procedures.
13. Ask the subject to complete the Subject Treatment Session Questionnaire (Appendix 4).
14. Complete the Reconstitution/Preparation Questionnaire (Appendix 1) and the Investigator Treatment Session Questionnaire (Appendix 2).
15. Schedule the next visit (Month 1  $\pm$ 7 days).

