### 6.1.7 Instructions for Use and Administration

In this study, Alluzience (50 s.U) will be compared to reference product powder BoNT-A (20 U) administered according to each products SmPC.

Alluzience is supplied as a liquid in a buffered solution. Powder BoNT-A is supplied as a white and dry substance that is reconstituted in sterile NaCl solution (saline) before use. For a description of the study products, see Section 6.1.3.

Both Alluzience and the saline used for reconstituting powder BoNT-A should be allowed to equilibrate to room temperature for 15 - 30 min before injection. The preparation of the syringe with Alluzience and the reconstitution of powder BoNT-A must be performed in the same room and in front of the subject by the Treating Investigator.

The injection procedure is identical for both treatment groups. In addition to being trained in the administration technique prior to study initiation, all Treating Investigators will need to have previous experience with BoNT-A products for the studied indication.

The handling of accidentally damaged or spilled study products are described in the Material Safety Data Sheets.

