## 14. APPENDICES

### Appendix 1 Preparation of Alluzience and Reconstitution of powder BoNT-A

#### Alluzience Preparation Questionnaire

Time for study product to equilibrate to room temperature

*(Note: should be 15 – 30 min according to CSP)*

     
MM:SS

How long did it take to prepare the product to have it ready for injection?

*Time from opening the outer box to having a syringe ready for use.*

     
MM:SS

Did you prepare the product in front of the subject?

Yes  No

I did not experience any technical issues/problems when using a ready to use product as compared to a product to be reconstituted

Strongly agree

Agree

Neither agree nor disagree

Disagree

Strongly disagree

	Title 05PF2005 Clinical Study Protocol - STAR	Doc id MA-48441
--	--	----------------------------------

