9.0 EFFICACY VARIABLES

9.1 Primary Efficacy Variables

To address the primary endpoint of evaluating the time needed to prepare Alluzience and powder BoNT-A according to protocol, the time (in minutes) needed to prepare Alluzience will be calculated as:

- Alluzience: The sum of the "Time for study product to equilibrate to room temperature" and the answer to the question "How long did it take to prepare the product to have it ready for injection?" on the Alluzience Reconstitution Questionnaire.

- Powder BoNT-A: The sum of the "Time for solvent to equilibrate to room temperature" and the answer to the question "How long did it take to prepare the product to have it ready for injection?" on the BOTOX/Vistabel Reconstitution Questionnaire.

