10.1 Primary Efficacy Analysis

The primary endpoint is the time (in minutes) needed to prepare Alluzience and powder BoNT-A according to protocol. CCI

[figure not shown]

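### The protocol gives two different equilibration times, and the SAP adds that wait to the primary preparation time, where it can outweigh the hands-on work

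*Protocol*

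**What the plan says.** Two instructions cover the same step and apply equally to Alluzience and to the saline for the powder.

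- Protocol 8.1.2, step 6 of the Visit 2 list: "Make sure to equilibrate Alluzience, or the saline used for reconstitution of powder BoNT-A, for 30 min to room temperature before injection".
- Protocol 6.1.7: both "should be allowed to equilibrate to room temperature for 15 - 30 min before injection".
- Both questionnaires in Protocol Appendix 1, and their copies in SAP Appendices B and C, print beside the entry field that the wait "should be 15 – 30 min according to CSP".

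The questionnaires also hold a separate field for the preparation work itself, described as "Time from opening the outer box to having a syringe ready for use". Both fields are recorded in minutes and seconds.

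SAP 10.1 states: "The primary endpoint is the time (in minutes) needed to prepare Alluzience and powder BoNT-A according to protocol". SAP 9.1 builds that time for Alluzience as "The sum of the 'Time for study product to equilibrate to room temperature' and the answer to the question" on preparation time. The powder arm uses the same construction, with the solvent's equilibration time in place of the product's.

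**The concern.** There are two linked problems.

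First, the protocol contradicts itself on a step that enters the primary variable. The endpoint is time to prepare according to protocol, but the protocol does not say consistently what that requires. The ambiguity reaches the per-protocol set. Membership depends on having no deviation with a substantial impact on the primary outcome (Protocol 9.1.1.2, SAP 5.2), and SAP 10.1.1 repeats the primary analysis on that set. Whether a 20-minute wait is a deviation cannot be settled from the text.

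Second, the protocol sets the wait, with the same range for both products. The study's rationale (Protocol 1.1 and 1.3) is that a ready-to-use solution avoids the work of reconstitution. The box-to-syringe field measures that work. Adding a wait that may differ by 15 min between subjects can hide a difference of a few minutes in the work.

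**Working it through.** The documents give no expected preparation time, SD, power or sample-size calculation, so there is no planned figure to reproduce.

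**Inputs from the documents:** waits of 15-30 min (Protocol 6.1.7, Appendix 1) and 30 min (Protocol 8.1.2); primary time T = E + P, where E is equilibration and P is box-to-syringe time (SAP 9.1); arms of 100 and 50 (Protocol 9.2).

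**Assumed inputs:** the distribution of E, and an SD of P from 0.5 to 2 min. The documents give neither.

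**1. Where the texts conflict.** A wait of exactly 30 min satisfies every passage. A wait from 15 to just under 30 min satisfies 6.1.7 and the questionnaires but not step 6. The range in dispute is 30 − 15 = 15 min. Section 6.1.7 alone allows the same 15-minute spread, with or without step 6.

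**2. How much of the sum is wait.** With E uniform on 15-30 min, SD(E) = 15/√12 = 4.33 and Var(E) = 18.75. Taking E and P as independent, Var(T) = 18.75 + SD(P)². The standard error of the arm difference is SD × √(1/100 + 1/50) = SD × 0.173.

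| SD(P), min | Share of Var(T) from wait | SE of difference, P alone | SE of difference, T |
|---|---|---|---|
| 0.5 | 18.75/19.00 = 99% | 0.09 | 0.75 |
| 1 | 18.75/19.75 = 95% | 0.17 | 0.77 |
| 2 | 18.75/22.75 = 82% | 0.35 | 0.83 |

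These figures describe a variable wait inside the endpoint. If every site followed step 6 exactly, the spread in E would be close to zero and this loss of precision would disappear.

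**3. Effect on the arm difference.** Suppose a share pA of one arm and pB of the other wait 30 min, and the rest wait 15 min. The difference in means then moves by 15 × (pA − pB).

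- Equal shares: 0 min.
- 60% vs 40%: 3 min.
- 75% vs 25%: 7.5 min.
- 100% vs 0%: 15 min.

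If half of each arm waits 30 min, the wait alone has an SD of 15 × √(0.5 × 0.5) = 7.5 min. Chance then moves the difference with a standard error of 7.5 × 0.173 = 1.30 min, or about ±2.5 min, ignoring stratification.

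**4. Effect on relative size.** Take assumed hands-on times of 2 and 5 min, a ratio of 2.5. A common 15-minute wait gives 17 vs 20 (ratio 1.18). A common 30-minute wait gives 32 vs 35 (ratio 1.09). The absolute difference stays at 3 min, but the relative difference nearly vanishes.

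**The case against.** A reader might infer that the contradictory instruction itself shifts the primary result by 15 min. The documents do not support that. The 15-30 min window allows the same spread without step 6, and 15 min is a ceiling for one subject or one arm's mean. Both texts treat the two products alike and randomization is stratified by site, so a site's consistent habit would largely cancel in the arm difference. Nothing in the documents suggests that the arms would follow different instructions. This objection stands, with one limit. The study is open-label, and the assignment is known at step 4, before the wait at step 6. Different waiting by arm is therefore possible, though not shown.

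The endpoint concerns preparation according to protocol, so counting a required step is defensible. The product labels are not available here, so the wait cannot be called irrelevant to either product. For this reason the sum should stay in the table, with its components shown beside it.

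The protocol plans descriptive analysis only (9.1.2.3, 9.1.4), so a standard error has limited bearing. That is fair, although means, SDs and medians still carry the wait. SAP Table 2 lists a change to Protocol 9.1.4, but its description is blacked out, so it cannot be said whether a formal test is planned.

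The text after the endpoint sentence in SAP 10.1 is also blacked out. It may already provide for separate reporting, so one cannot conclude that the SAP omits it. The recorded waits will in any case show any divergence.

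**Conclusion.** The point holds in two parts. The contradiction between Protocol 8.1.2 step 6 and Protocol 6.1.7 with the questionnaires is plain on the page, and it leaves protocol compliance and per-protocol status unclear for any wait from 15 to just under 30 min. Separately, the SAP 9.1 definition puts a wait that may vary by up to 15 min per subject into the primary variable.

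The 82-99% variance share and the rise in standard error rest on an assumed uniform wait, independent of hands-on time, and an assumed hands-on SD of 0.5-2 min. They measure the cost of including a variable wait and should not be attributed to the conflict. The arm difference moves by the full 15 min only if one arm always waits 15 min and the other always 30 min; with common site habits the shift should be near zero.

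Confidence is medium, because part of SAP 10.1 cannot be read. The change should be made, but nothing here invalidates the trial.

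**What to change.** Reconcile Protocol 8.1.2 step 6, Protocol 6.1.7, the two questionnaires in Protocol Appendix 1 and their copies in SAP Appendices B and C, so that one equilibration instruction applies to both arms and all sites. This review takes no position on which time is right. Agreeing on the 15-30 min window would settle compliance but leave the spread in the sum, so the reporting change is needed as well.

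In SAP 9.1 and 10.1, report the box-to-syringe time and the equilibration time separately by arm, alongside the sum, unless the blacked-out text of SAP 10.1 already does this. State before database lock which waits count as deviations for the per-protocol set.

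The cost is one corrected protocol instruction, with matching form text if needed, and two extra rows in the primary table. Both components are already collected.

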## SCHEDULE OF ASSESSMENTS

**Table 2 Schedule of Assessments**

1 month = 4 weeks/28 days Visit windows are calculated from Baseline/Visit 2 if not otherwise specified.	Visit 1 Group 1 and 2	Visit 2 Group 1 and 2	Visit 3/ Group 1 EoS Group 2	Visit 4 Group 1	Visit 5 Group 1	Visit 6/ET EoS Group 1
	Screening 	Treatment/ Baseline  (within 3 weeks after screening)	1-Month Follow-up (±7 days)	3-Month Follow-up (±7 days)	5-Month Follow-up (±7 days)	6-Month Follow-up (±7 days)
Informed Consent	X	(X) 				
Demographic Data including, medical history & con-current diseases, previous facial treatments/ procedures	X	(X) 				
Inclusion /Exclusion Criteria	X	X				
Adverse Events 		X	X	X	X	X
Concomitant Medication/ Procedures	X	X	X	X	X	X
Urine Pregnancy Test 	X	X				
Photography		X	X	X		X
Randomization		X				
Treatment		X				
End of study 			X Group 2, powder BoNT-A			X Group 1, Alluzience
Investigator Assessments						
Reconstitution/Preparation Questionnaire		X				
Investigator Treatment Session Questionnaire 		X				
CCI						

1. Screening and treatment/baseline visits can be performed at the same day
2. Only to be conducted if no screening visit has been performed. Changes to medical history should be asked for if the screening and baseline visits are not performed on the same day.
3. AEs are collected from treatment to the end of the subject's participation, for details how to follow-up ongoing AEs at the last visit see section [7.2.1.1.5](#).
4. Only for women of childbearing potential
5. Subjects in the powder BoNT-A treatment group will be followed 1 month and subjects in the Alluzience treatment group will be followed for 6months.
6. Only for Alluzience-treated subjects
7. Only to be completed once for each Treating Investigator, per study product, after all enrolled subjects have completed Visit 2.
8. Performed pre-treatment

CONFIDENTIAL

Page 17 of 71

*Effective*

GALDERMA EST. 1981	Title 05PF2005 Clinical Study Protocol - STAR	Doc id MA-48441
-----------------------	---	---------------------------

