#### 5.2.1 Inclusion Criteria

Subjects must meet all the following criteria to be eligible for the study:

1. Female 18 to < 65 years of age.
2. Moderate to severe GL at maximum frown as assessed by the Investigator.
3. Female of non-childbearing potential (i.e., postmenopausal [absence of menstrual bleeding for 1 year prior to screening, without any other medical reason], or has undergone hysterectomy or bilateral oophorectomy).

OR

Female of childbearing potential with a negative urine pregnancy test at screening and baseline and agrees to use a highly effective and approved contraceptive method for the duration of the study. A highly effective method of contraception is defined as:

CONFIDENTIAL

Page 29 of 71

GALDERMA EST. 1981	Title 05PF2005 Clinical Study Protocol - STAR	Doc id MA-48441
-----------------------	---	---------------------------

Effective date: 2021-12-01 17:39

Effective

Version: 5.0

- Bilateral tubal ligation;
- Combined (estrogen and progesterone containing) oral, intravaginal or transdermal contraceptives that inhibit ovulation as the primary mode of action, on a stable dose for at least 28 days prior to screening visit;
- Hormonal or copper IUD inserted at least 28 days prior to Day 1;
- Partner vasectomized for at least three months prior to screening visit;
- Progestogen-only oral, injectable or implantable contraceptives that inhibit ovulation as the primary mode of action, on a stable dose for at least 28 days prior to screening visit; or
- Strict abstinence (i.e., refraining from heterosexual intercourse for the entire duration of the subject's participation in the study).

4. Time and ability to complete the study and comply with instructions.
5. Understands the study requirements and signed the informed consent form (ICF).
6. Subjects who have planned to undergo aesthetic facial treatment with powder toxin at the study site.
7. Previous use of any approved botulinum toxin in facial areas.

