### 6.4 Blinding

Not applicable – open-label study.

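### The pre-treatment subject satisfaction form is scheduled after open-label randomization, so a subject may already know the assigned product when giving the baseline answer

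*Protocol*

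**What the plan says.** Protocol Section 8.1.2 is a numbered list. At step 3 eligibility is confirmed: "If yes, enroll/randomize the subject in the clinical study. Proceed to the next steps". At step 4, "the Investigator will receive notification of the subject's randomization assignment". Step 5 is photography. Step 6 differs by arm: "Make sure to equilibrate Alluzience, or the saline used for reconstitution of powder BoNT-A, for 30 min to room temperature before injection". Step 7 is the form at issue: "Ask the subject to complete the Subject Satisfaction Questionnaire (Appendix 6"), with a note that it "must be performed before treatment". Step 8 is preparation of the assigned product in the subject's presence, and step 10 is the injection.

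Three other places bear on this. Section 6.4 disposes of blinding with "Not applicable – open-label study". Inclusion criterion 6 in Section 5.2.1 admits "Subjects who have planned to undergo aesthetic facial treatment with powder toxin at the study site". Footnote 8 of Table 2, repeated in SAP Appendix A, says "Performed pre-treatment"; the row it marks is redacted.

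**The concern.** A baseline is most useful when it describes the subject before assignment can influence the answer. Here the form is a self-report, the assignment is already known at the site, and nothing in the visible text stops the subject from learning it first. The population makes a reaction plausible: every subject had planned a powder product and had used a botulinum toxin before (inclusion criteria 6 and 7), so allocation to the liquid product departs from what she came for.

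If knowing the arm changes the answer, assignment itself causes the difference at baseline. Randomization cannot balance such a difference, because it arises after randomization. Any summary that uses the form as a baseline, whether a change from baseline or a comparison of the groups at entry, would contain it. Subject perception of the treatment session is part of the overall objective in Protocol Section 2.1, and Alluzience subjects are followed for 6 months.

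**Working it through.** There is no figure in the plan to reproduce. The sample size has no statistical basis (Protocol Section 9.2), and the point concerns the order of procedures. The check sets the steps of Section 8.1.2 in order and asks who can know the assignment at each.

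| Step | Procedure | Assignment known to |
|---|---|---|
| 3 | Randomization in the web system (also Section 6.1.5) | System |
| 4 | Notification | Investigator |
| 5 | Photographs | Investigator; subject not stated |
| 6 | Equilibration of Alluzience, or of saline for the powder | Site staff; subject not stated |
| 7 | Subject Satisfaction Questionnaire | Site staff; subject not stated |
| 8 | Preparation in front of the subject | Subject can see it |
| 10 | Treatment | All |

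1. **Order.** The form (7) precedes treatment (10) but follows randomization (3), notification (4) and the arm-specific step (6).
2. **Timing rule.** The note at step 7 refers only to treatment. A form completed during step 8, with the product in view, would depart from the numbered order but still satisfy the note.
3. **Protection of the answer.** Sections 6.1.5, 6.4 and 8.1.2 contain no instruction to withhold the assignment from the subject. The equilibration wait (30 minutes in Section 8.1.2, 15 to 30 minutes in Section 6.1.7 and Appendix 1) gives time for it to become known.
4. **Effect on a change score, if one is planned.** Let d0 be the shift in the baseline answer caused by knowing the product, and d1 the corresponding shift at follow-up. The observed change equals the change without such shifts plus (d1 − d0). If d1 = 0, the distortion is −d0. If the shift persists unchanged, d1 = d0 and the distortion is zero. The documents give neither d0 nor d1, so neither size nor sign follows.
5. **Endpoints affected.** The primary endpoint is preparation time (Protocol Section 2.1.1). The visible secondary endpoints come from the preparation questionnaires and the Investigator Treatment Session Questionnaire (Section 2.1.2). None uses the subject satisfaction form.

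**The case against.** The strongest reply is that contamination is not shown. Step 4 informs the Investigator only, and the first step that must take place before the subject's eyes is step 8, after the form. That stands: subject knowledge at step 7 is possible under the open-label design, not established. The point is therefore about a risk left open.

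A reader might infer that any shift at baseline passes in full into the change from baseline. The documents do not support this. No change-from-baseline analysis of this form is visible, and full carry-over needs the shift to be absent at follow-up, which is also open-label. If the shift persists, a baseline taken before randomization would leave d1 in the change score. The fix therefore does not remove open-label reporting effects at follow-up. It does give a baseline that assignment cannot have influenced.

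A reader might also infer a biased comparison between arms over time. Powder subjects leave at Month 1, and redacted Month 1 text stands under the Alluzience item of Section 8.1.3. Follow-up satisfaction may thus be collected in the Alluzience group only. That is an inference, but it makes a within-Alluzience change the likelier place for any harm.

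Finally, the analysis may be purely descriptive (Protocol Sections 9.1.2.3 and 9.1.4). This is not certain: SAP Section 11.1 refers to statistical tests among the secondary analyses, and SAP Section 16 lists a change to Protocol Section 9.1.4. Which outcomes are tested is redacted. A biased baseline would in any case also distort a descriptive summary.

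**Conclusion.** The point holds as an avoidable risk of bias confined to analyses that use the pre-treatment satisfaction form. It rests on the step order, the absence of a rule beyond precedence over treatment, and the open-label design. For the risk to become an actual bias, the subject must learn the assignment before step 7 and that knowledge must alter her answers; neither is documented.

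No magnitude can be given. The items, endpoint and analysis are redacted, and the documents offer no basis for assuming a shift of any particular size. It would be too strong to call the order an error whatever the redacted endpoint is. Nor does the argument extend to the baseline photographs at step 5: the mechanism is altered self-report, and the documents suggest no way in which allocation would change a standardized photograph. The visible primary and secondary results are not at risk. This is a modest improvement that is cheap enough to make.

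**What to change.** In Protocol Section 8.1.2, have the Subject Satisfaction Questionnaire completed after eligibility is confirmed and before the randomization call in step 3. If the sponsor prefers to use the equilibration wait for the form, keep it at step 7 but add a requirement that the assignment not be disclosed to the subject until the form is complete. If footnote 8 of Table 2 and of SAP Appendix A marks this questionnaire, reword it to match.

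The first option may add a few minutes to Visit 2, because the form may no longer overlap with equilibration of the assigned material. The second keeps the overlap but relies on site discipline in an open-label setting. Neither needs a new assessment, a new visit or a change in sample size.
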